#### 5.1.3 Treatment and trial completers

A subject who has not permanently discontinued IMP before Week 16 will be defined as a treatment completer.

A subject is considered to have completed the trial if they have completed all periods of the trial including the safety follow-up visit (Week 20).

#### 5.1.4 Early termination and unscheduled visits

When no data are available from a certain scheduled post-baseline visit for a subject, data from early termination visits and unscheduled visits may replace data from that scheduled visit in data summaries, provided the data are collected between 6 days before and 7 days after the planned time point for the scheduled visits, as given in [Panel 4](#).

When both unscheduled and early termination visits exist within the given visit window, the early termination visit will be selected for analysis. When no early termination visits and several unscheduled visits exist, the unscheduled visit closest to the target day will be selected for analysis. If the difference is a tie, the latest unscheduled visit will be selected.

THIS DOCUMENT CONTAINS CONFIDENTIAL INFORMATION AND MUST NOT BE COPIED OR MADE AVAILABLE TO ANY THIRD PARTY WITHOUT THE PRIOR WRITTEN CONSENT OF THE LEO PHARMA GROUP

#### Panel 4: Visit windows

Visit (target day)	Visit window (day is date of assessment minus date of first dose)
Week 2 (Day 14)	Day 8 to 21
Week · (Day $7 \cdot x$ , where $x = 4, 6, 8, \dots, 16$ )	Day $7 \cdot x - 6$ to $7 \cdot x + 7$
SFU	36-49 days after last dose

#### 5.2 Extent of exposure

Exposure time will be presented as patient years of exposure (PYE) and will be calculated as the difference between the exposure start date and time and the exposure end date and time and divided by  $60 \cdot 60 \cdot 24 \cdot 365.25$ . Exposure start date and time and exposure end date and time are defined in [Panel 3](#), Section [5.1.2](#).

Exposure time will be summarized and listed for the safety analysis set. The summaries will be using descriptive statistics for continuous data as well as number and percentage of subjects with less than 6 weeks of exposure time, 6-11 weeks of exposure time, 12-15 weeks of exposure time, and  $\geq 16$  weeks of exposure time.

#### 5.3 Intercurrent events

Two intercurrent events are considered to affect the interpretation of the estimates of the endpoints:

- **Initiation of rescue treatment:** This event occurs when a subject initiates rescue treatment. This event can occur at the discretion of the investigator. The timing of the event is defined as the date of initiation of the rescue treatment recorded in the eCRF.

Rescue treatment will be defined by the following algorithm: Concomitant medications with 'Dermatitis atopic' or 'Dermatitis infected' as the preferred term for the indication and either of the following:

1. ATC2 code H02 or D07.
2. ATC4 code D11AH.
3. Preferred name:
  - delgocitinib,
  - crisaborole,
  - methotrexate,
  - ciclosporin,
  - azathioprine,

THIS DOCUMENT CONTAINS CONFIDENTIAL INFORMATION AND MUST NOT BE COPIED OR MADE AVAILABLE TO ANY THIRD PARTY WITHOUT THE PRIOR WRITTEN CONSENT OF THE LEO PHARMA GROUP

- mycophenolate-mofetil,
- mycophenolate-sodium,
- mycophenolate-acid,
- ruxolitinib,
- dupilumab,
- upadacitinib or
- abrocitinib

- **Permanent discontinuation of IMP:** This event occurs when a subject is permanently withdrawn from treatment or the trial. This event can occur at the subject's own initiative, at the discretion of the investigator or the sponsor, or if the subject is lost to follow-up.

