11. Subjects must have applied a stable dose of emollient twice daily (or more, as needed) for at least 14 days before baseline.
12. A woman of childbearing potential* must use a highly effective** form of birth control throughout the trial and at least for 16 weeks (5 half-lives) after last administration of IMP.

*A woman of childbearing potential is defined as a female subject, who at the discretion of the investigator, is deemed to be of reproductive potential. A woman is defined as not being of childbearing potential if she is postmenopausal (at least 12 months with no menses without an alternative medical cause prior to screening), or surgically sterile (hysterectomy, bilateral salpingectomy, or bilateral oophorectomy).

**A highly effective method of birth control is defined as one which results in a low failure rate (less than 1% per year) such as bilateral tubal occlusion, intrauterine device (IUD), intrauterine hormone-releasing system (IUS), combined (oestrogen- and progestogen-containing) hormonal contraception associated with inhibition of ovulation (oral, intravaginal, transdermal), progestogen-only hormonal contraception associated with inhibition of ovulation (oral, injectable, implantable), sexual abstinence (when this is in line with the preferred and usual life style of the subject

and not just being without a current partner), same-sex partner, or vasectomised partner (given that the subject is monogamous).

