9.5 Rescue treatment

If medically necessary (i.e. to control intolerable AD symptoms), rescue treatment for AD may be provided to trial subjects at the discretion of the investigator. If possible, investigators should attempt to limit the first step of rescue therapy to topical medications (i.e. TCS/TCI) and escalate to systemic medications only for subjects who do not respond adequately after at least 14 days of topical treatment.

Subjects who receive topical rescue treatment will continue IMP treatment.

If a subject receives rescue treatment with systemic corticosteroids or non-steroidal systemic immunosuppressive drugs (methotrexate, mycophenolate mofetil, azathioprine, etc.), IMP will be immediately discontinued. After the treatment with these medications is completed, IMP

THIS DOCUMENT CONTAINS CONFIDENTIAL INFORMATION AND MUST NOT BE COPIED OR MADE AVAILABLE TO ANY THIRD PARTY WITHOUT THE PRIOR WRITTEN CONSENT OF THE LEO PHARMA GROUP

may be resumed if deemed appropriate by the investigator, but not sooner than 5 half-lives after the last dose of systemic rescue treatment. The use of biological rescue treatment will be disallowed for the entire trial duration.

Investigators should make every attempt to conduct efficacy and safety assessments (at least disease severity scores [IGA and EASI], concomitant medications/procedures, and AEs) immediately before administering any rescue treatment. An unscheduled visit may be used for this purpose, if necessary.

Use of rescue medication will be recorded in the eCRF.

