9.6 Concomitant medication and concurrent procedures

Any medication or vaccine that the subject receives from 3 months prior to screening through safety follow-up must be recorded in the subject's medical record and the eCRF along with details such as:

- Medication name.
- Indication.
- Start and stop date of administration (it will also be recorded if the medication is ongoing).
- Dosage information, including dose per administration, unit, and frequency.
- Route of administration.

Similarly, any concurrent procedure must also be recorded in the subject's medical record and the eCRF. Note that in this trial, only surgical procedures and procedures related to AD treatment (e.g. phototherapy or bleach baths) should be recorded. The following details will be recorded: procedure, body location, indication, and start and stop date (it will also be recorded if the procedure is ongoing).

Investigators may prescribe concomitant medications or treatments to provide adequate supportive care as deemed necessary, except for medications listed in Section 9.7. The sponsor's medical expert should be contacted if there are any questions regarding concomitant or prior therapy.

The following concomitant medications related to AD treatment are permitted from screening through the safety follow-up period (Week 20):

THIS DOCUMENT CONTAINS CONFIDENTIAL INFORMATION AND MUST NOT BE COPIED OR MADE AVAILABLE TO ANY THIRD PARTY WITHOUT THE PRIOR WRITTEN CONSENT OF THE LEO PHARMA GROUP

- Oral antibiotics, antiviral, or antifungal therapy for skin infections as appropriate.
- Stable doses of an emollient (see Section 9.4; subjects must apply emollient twice daily [or more, as needed] for at least 14 days before baseline and throughout trial participation).
- Oral antihistamines.

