9.7 Prohibited medications and procedures

The medications and procedures listed below are prohibited during the trial from baseline (Week 0). Details regarding prohibited medications and procedures prior to baseline are described in Section 8.3.

From baseline through end of treatment (Week 16):

- TCS of any potency (unless for rescue treatment, see Section 9.5).
- Other topical medications used for the treatment of AD, such as TCI and topical PDE-4 inhibitors.
- Use of UVA or UVB, psoralen + UVA (PUVA), other phototherapy, or tanning beds.
- 3 or more bleach baths per week.

From baseline through safety follow-up (Week 20):

- Investigational agents other than tralokinumab.
- Systemic corticosteroids (nasal, ophthalmic, and inhaled corticosteroids are allowed).
- Systemic treatment for AD with an immunosuppressive/immunomodulating agent (e.g. cyclosporine A, mycophenolate mofetil, azathioprine, methotrexate, JAK inhibitors, interferon-gamma, dupilumab, or other biologics).
- Allergen immunotherapy.
- Live (attenuated) vaccine*.
- Immunoglobulins.
- Blood products.

THIS DOCUMENT CONTAINS CONFIDENTIAL INFORMATION AND MUST NOT BE COPIED OR MADE AVAILABLE TO ANY THIRD PARTY WITHOUT THE PRIOR WRITTEN CONSENT OF THE LEO PHARMA GROUP

*Receipt of inactive/killed vaccines (e.g. inactive influenza) is allowed, provided it is not administered in the same location as tralokinumab.

Some of the above mentioned prohibited medications can be used provided the indication is rescue treatment for AD. Please refer to Section 9.5 for details regarding rescue treatment.

In case any prohibited treatments are used during the trial, they must be recorded as concomitant medication in the eCRF.

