10.2.2 Reasons for temporary discontinuation of IMP

IMP dosing may be temporarily suspended in the event of:

- Other intercurrent illness or major surgery.
- An infection that requires parenteral treatment with antibiotic, antifungal, antiviral, anti-parasitic, or anti-protozoal agents.

IMP dosing should be temporarily suspended in the event of:

- Treatment with systemic corticosteroids or non-steroidal immunosuppressive/immunomodulating medications (e.g. cyclosporine, methotrexate, azathioprine, mycophenolate mofetil, JAK inhibitors, dupilumab, or other biologics).

After the treatment with these medications is completed, IMP may be resumed if deemed appropriate by the investigator, but not sooner than 5 half-lives after the last dose of systemic rescue treatment.

THIS DOCUMENT CONTAINS CONFIDENTIAL INFORMATION AND MUST NOT BE COPIED OR MADE AVAILABLE TO ANY THIRD PARTY WITHOUT THE PRIOR WRITTEN CONSENT OF THE LEO PHARMA GROUP

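### Beyond three ATC codes, the rescue rule finds systemic immunosuppressants, JAK inhibitors and biologics only by drug name, so an unmatched drug given for AD does not by itself make a subject a non-responder

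*SAP*

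**What the plan says.** SAP 5.3 makes rescue a matter of definition by algorithm. The record must be one of "Concomitant medications with 'Dermatitis atopic' or 'Dermatitis infected' as the preferred term for the indication and either of the following": (1) ATC2 H02 or D07; (2) ATC4 D11AH; (3) a preferred name from a list of 12. Protocol 14.3.4 has the same indication terms and codes, and 10 names. SAP Panel 11 records that upadacitinib and abrocitinib were added because they had since been approved. Neither text has a catch-all, an investigator flag or a medical-review step.

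The clinical sections use wider terms. Protocol 9.5 refers to systemic corticosteroids and "non-steroidal systemic immunosuppressive drugs (methotrexate, mycophenolate mofetil, azathioprine, etc", an open-ended list. Protocol 9.7 prohibits systemic AD treatment with agents that include "JAK inhibitors, interferon-gamma, dupilumab, or other biologics". Protocol 10.2.2 suspends the trial drug for much the same classes, and says that "IMP may be resumed if deemed appropriate by the investigator, but not sooner than 5 half-lives after the last dose of systemic rescue treatment".

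Under SAP 1.1 and 5.4.2 the composite rule sets a subject to non-response for rescue as defined, for permanent discontinuation of the trial drug, or for a missing Week 16 assessment. The stated reason is that these events signal treatment failure or a response that cannot be credited to the trial drug alone.

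**The concern.** The composite estimand does what it says only if the algorithm finds the treatments it is meant to find. The algorithm is a closed list, while the protocol describes the treatments by class. The list has already needed two additions as products were approved. It also includes dupilumab, although Protocol 9.5 disallows biological rescue. So it is evidently meant to catch disallowed agents too, yet it names only one biologic.

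A responder at Week 16 who took an unmatched systemic drug for AD would be counted as a success for the autoinjector, against the plan's own rationale. The same rule feeds both primary endpoints, the subgroup analysis by baseline IGA and the other binary efficacy endpoints. The continuous endpoints are presented as observed and are not affected. With one arm and no formal testing, the rates and their intervals are the efficacy result, and the adult results are intended to support a marketing submission (SAP 5.9).

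**Working it through.** **1. Contents of the rule.** Three ATC codes (two at level 2, one at level 4). SAP names: 12. Protocol names: 10. Difference: upadacitinib and abrocitinib. Every individual drug named in Protocol 9.5 and 10.2.2 is on the list. Interferon-gamma is the only agent named in 9.7 that is not listed by name.

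**2. Routes to non-response for an unmatched systemic drug given for AD.**

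- Rescue: not triggered, because the algorithm is the definition.
- Permanent discontinuation: not automatic. Protocol 10.2.2 makes the suspension temporary, and SAP Panel 3 defines a discontinuation date only where a reason for permanent discontinuation was recorded.
- Missing Week 16 data: does not apply if the subject attends.
- Earlier topical rescue: would trigger the rule, assuming that D07 and D11AH cover TCS and TCI. Protocol 9.5 asks investigators, if possible, to start with topicals and "escalate to systemic medications only for subjects who do not respond adequately after at least 14 days of topical treatment". This catches some subjects, not necessarily all.

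Two cases remain: (a) the trial drug is suspended but no permanent discontinuation is recorded; (b) the drug is started after the Week 14 dose, which is the last one, and before Week 16. In case (b) there is no further dose to withhold, and the end-of-treatment form (Protocol 11.8) asks only about permanent discontinuation before Week 14.

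**3. The plan's precision, reproduced.** Inputs from Protocol 14.1: N = 130, p = 0.19 (IGA 0/1) and 0.29 (EASI75). SE = √(p(1 − p)/N); half-width = 1.96 × SE.

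- IGA 0/1: √(0.19 × 0.81/130) = 3.44%; half-width 6.74%.
- EASI75: √(0.29 × 0.71/130) = 3.98%; half-width 7.80%.

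Both agree with the protocol.

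**4. Direction and size.** If x responders are counted and k of them took an unmatched drug, the rate under the stated rationale is (x − k)/N. Since k is zero or more, the reported x/N is right or too high. Shift per affected responder: 1/130 = 0.77 points; 1/100 = 1.0 (adults, 130 − 30); 1/30 = 3.3 (adolescents).

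**5. Effect on the intervals.** Wilson limits, as in SAP 5.1: [p + z²/2n ± z√(p(1 − p)/n + z²/4n²)]/(1 + z²/n), with z = 1.96. Counts are the assumed rates times N, rounded: 0.19 × 130 = 24.7, taken as 25; 0.29 × 130 = 37.7, taken as 38; 0.19 × 30 = 5.7, taken as 6. The documents give no value for k, so k = 0 to 3 is an assumed range.

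| Endpoint | k | Rate | Wilson 95% CI |
|---|---|---|---|
| IGA 0/1, all | 0 | 25/130 = 19.23% | 13.38 to 26.85 |
| | 1 | 24/130 = 18.46% | 12.73 to 26.00 |
| | 3 | 22/130 = 16.92% | 11.45 to 24.30 |
| EASI75, all | 0 | 38/130 = 29.23% | 22.10 to 37.56 |
| | 1 | 37/130 = 28.46% | 21.41 to 36.75 |
| | 3 | 35/130 = 26.92% | 20.04 to 35.13 |
| IGA 0/1, adolescents | 0 | 6/30 = 20.00% | 9.51 to 37.31 |
| | 1 | 5/30 = 16.67% | 7.34 to 33.56 |

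Over the assumed range the overall shift is 0 to 2.3 points (3/130), against planned half-widths of 6.74 and 7.80.

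**The case against.** The strongest reply has four parts.

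- **No escaping drug is shown.** The documents do not say what H02, D07 and D11AH cover, so even interferon-gamma cannot be shown to escape. This stands. It limits the point to a mismatch in definitions, not a demonstrated misclassification.
- **Protocol 9.7 and 10.2.2 are management rules, not definitions of rescue, and biological rescue is disallowed.** This is fair as far as it goes. But 9.5 itself leaves systemic rescue open-ended, and listing dupilumab shows that the algorithm is meant to reach disallowed agents.
- **The rule that IMP may resume only after five half-lives closes the gap.** A reader might infer this, since a long-acting drug would rule out any return to treatment. It does not follow. Not resuming becomes non-response only if the site records permanent discontinuation, and the rule has no bearing on a drug started after the Week 14 dose.
- **Broadening the definition late in an open-label trial is hard to police.** SAP 5.9 says there is no blinding to maintain, and under Appendix 3D the sponsor sees eCRF data as soon as they are entered. This is a real cost. It is contained by deriving the list from drug classes alone, fixing it before the lock, and publishing the number reclassified, from which a reader can see how far the change could have moved the result.

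**Conclusion.** The rule has a narrow gap. Apart from the three ATC codes, systemic immunosuppressive or immunomodulating drugs, JAK inhibitors and biologics are caught only by name, and an unmatched one given for AD does not by itself produce non-response. Any error is upward only, at 0.77 points per affected responder at N = 130, 1.0 among about 100 adults and 3.3 among 30 adolescents. The frequency cannot be derived from the documents. It is probably small, given the topical-first step and the other two routes to non-response. This is an optional, inexpensive improvement.

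Two stronger readings are not supported. One is that the algorithm has no class-level terms at all: ATC codes are class codes, and no gap is shown for systemic corticosteroids, TCS or TCI. The other is that AD phototherapy, which 9.7 prohibits and 9.6 asks sites to record, is wrongly left out. Protocol 9.5 describes rescue as medication, so counting a procedure would extend the definition, not correct it.

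**What to change.** In SAP 5.3, keep the indication requirement, the codes, the names and the existing timing rules, including the Protocol 14.3.4 rule for rescue started on the day of an assessment. Add one class term: any other systemic immunosuppressive or immunomodulating drug given for one of the listed indications, including JAK inhibitors and biologics other than the trial drug. Before the interim database lock, turn that term into a fixed list of coded drugs without reference to IGA or EASI data, so that the rule remains an algorithm. Log the change in Panel 11 and report how many subjects it reclassifies, even if that is none.

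The cost is a line of SAP text, one coded list and one count. No new data are needed, because Protocol 9.7 already requires prohibited treatments to be recorded as concomitant medication. The downside is some minor coding judgement and possibly a slightly lower response rate. What patients may receive does not change.

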8.3 Exclusion criteria

Subjects are not eligible for the trial if they violate any of the following criteria:

1. Concurrent enrolment in another interventional clinical trial.
2. Previous randomisation in a tralokinumab clinical trial.
3. Active dermatologic conditions that may confound the diagnosis of AD or would interfere with assessment of treatment, such as scabies, cutaneous lymphoma, or psoriasis.
4. Known active allergic or irritant contact dermatitis that is likely to interfere with the assessment of severity of AD.
5. Use of tanning beds or phototherapy (narrow band ultraviolet B [NBUVB], ultraviolet B [UVB], ultraviolet A1 [UVA1], psoralen+ultraviolet A [PUVA]) within 4 weeks prior to baseline.
6. Treatment with the following medications within 4 weeks prior to baseline:
 - Systemic immunosuppressive/immunomodulating drugs (e.g. methotrexate, cyclosporin A, azathioprine, mycophenolate mofetil, Janus kinase (JAK) inhibitors).
 - Systemic corticosteroid use (excludes topical, inhaled, or intranasal delivery).
 - Three or more bleach baths during any week within the 4 weeks.
7. Treatment with the following medications within 2 weeks prior to baseline:
 - TCS.
 - TCI.
 - Topical PDE 4 inhibitors.
 - Topical JAK inhibitors.
8. Receipt of live attenuated vaccines within 30 days prior to the date of baseline and during the trial including the safety follow-up period.
 - Receipt of inactive/killed vaccinations (e.g. inactive influenza) is allowed but it should not be administered in the same location as tralokinumab.

THIS DOCUMENT CONTAINS CONFIDENTIAL INFORMATION AND MUST NOT BE COPIED OR MADE AVAILABLE TO ANY THIRD PARTY WITHOUT THE PRIOR WRITTEN CONSENT OF THE LEO PHARMA GROUP

9. Receipt of any marketed biological therapy (i.e. immunoglobulin, anti-IgE) including dupilumab or investigational biologic agents:
 - Any cell-depleting agents including but not limited to rituximab: within 6 months prior to baseline, or until lymphocyte count returns to normal, whichever is longer.
 - Other biologics: within 3 months or 5 half-lives, whichever is longer, prior to baseline.
10. Receipt of any investigational non-biologic agent within 5 half-lives prior to baseline.
11. Receipt of blood products within 4 weeks prior to screening.
12. Major surgery within 8 weeks prior to screening or planned in-patient surgery or hospitalisation during the trial period.
13. Known or suspected allergy or reaction to any component of the IMP formulation.

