14.1 Sample size

Approximately 130 subjects, of which approximately 30 subjects will be adolescents, will be assigned to treatment. This is considered sufficient to allow an evaluation of the efficacy of tralokinumab.

Assuming IGA 0/1 and EASI75 response rates of 19% and 29% at Week 16, respectively, a sample size of 130 subjects will give a standard error of 3.44% and 3.98%, and thus a half-width for the 95% CIs of 6.74% and 7.80% for each of the primary endpoints.

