**Abbreviations:** AD = atopic dermatitis; ADA = anti-drug antibodies; AEs = adverse events; CDLQI = Children's Dermatology Life Quality Index; DLQI = Dermatology Life Quality Index; EASI = Eczema Area and Severity Index; EASI90/EASI75/EASI50 = at least 90% / 75% / 50% reduction in EASI score; HRQoL = health-related quality of life; IGA = Investigator's Global Assessment; IMP = investigational medicinal product; NRS = numeric rating scale; POEM = Patient-Oriented Eczema Measure.

THIS DOCUMENT CONTAINS CONFIDENTIAL INFORMATION AND MUST NOT BE COPIED OR MADE AVAILABLE TO ANY THIRD PARTY WITHOUT THE PRIOR WRITTEN CONSENT OF THE LEO PHARMA GROUP

The primary endpoints will be analysed using a composite estimand strategy to handle the occurrence of two intercurrent events considered to affect the interpretation of the estimates of the endpoints (initiation of rescue medication and permanent discontinuation of IMP).

The composite estimand evaluates the response rate without initiation of rescue treatment or permanent discontinuation of IMP. For subjects who received rescue treatment prior to Week 16 or who have permanently discontinued IMP prior to Week 16, observed data after the intercurrent events will be considered non-response, reflecting an assumption that initiation of rescue treatment or permanent discontinuation of IMP indicates either failure of the treatment to achieve response or that a possible positive response is not attributable to the treatment alone. Missing data for subjects who do not attend the Week 16 visit and where rescue medication has not been used, nor the subject has permanently discontinued IMP, will be imputed as non-response.

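### The rescue rule misses phototherapy given for AD, and systemic corticosteroids given for another indication, so a Week 16 response obtained with either can be credited to tralokinumab

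*SAP*

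**What the plan says.** SAP 5.3 names two intercurrent events: initiation of rescue treatment and permanent discontinuation of IMP. A subject has had rescue only if two conditions hold together. The first is "Concomitant medications with 'Dermatitis atopic' or 'Dermatitis infected' as the preferred term for the indication and either of the following". The second is ATC2 code H02 or D07, ATC4 code D11AH, or a drug name on a fixed list. Protocol 14.3.4 has the same structure; the SAP adds two drug names.

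SAP 1.1 gives the reason for counting these events as non-response. They indicate either treatment failure or that "a possible positive response is not attributable to the treatment alone".

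The protocol restricts both treatments at issue:

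- **Phototherapy.** Excluded for 4 weeks before baseline (Protocol 8.3, criterion 5). Protocol 9.7 prohibits from baseline to Week 16 "Use of UVA or UVB, psoralen + UVA (PUVA), other phototherapy, or tanning beds". On concurrent procedures, Protocol 9.6 says "only surgical procedures and procedures related to AD treatment (e.g. phototherapy or bleach baths) should be recorded". Protocol 9.7 separately asks that prohibited treatments be entered as concomitant medication.
- **Systemic corticosteroids.** Protocol 8.3, criterion 6, excludes for 4 weeks before baseline "Systemic corticosteroid use (excludes topical, inhaled, or intranasal delivery"), with no limit by indication. Protocol 9.7 prohibits them to Week 20, again with no such limit. Protocol 10.2.2 lists "Treatment with systemic corticosteroids or non-steroidal immunosuppressive/immunomodulating medications" as a reason for temporary suspension of IMP.

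**The concern.** The response rule is narrower than the protocol's own view of which treatments matter. Two conditions cause this: the rule looks only at medications, and it looks only at two indication terms. Adding further drug names, as the SAP did for upadacitinib and abrocitinib, removes neither.

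A subject could have phototherapy for AD in the weeks before Week 16 and still be scored as an IGA 0/1 or EASI75 responder. A subject could also take a systemic corticosteroid for some other disease, have IMP suspended but not permanently discontinued, and be scored as a responder. With one arm, no comparator absorbs such cases. They go straight into the rate reported for the autoinjector, and into the adult interim report that SAP 5.9 says will support a marketing submission.

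**Working it through.** **Step 1: put each case through the rule.**

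| | AD phototherapy | Systemic corticosteroid, non-AD indication |
|---|---|---|
| Concomitant medication? | Procedure under Protocol 9.6; possibly also a medication entry under 9.7 | Yes |
| AD or infected-dermatitis indication? | Yes, if entered as a medication | No |
| Listed code or name? | Not named on the list | H02 is listed, but the indication condition has already failed |
| Counted as rescue? | No | No |
| Effect on IMP | None stated | Temporary suspension (10.2.2), which is not an intercurrent event |
| Other route to non-response | Permanent discontinuation only | Permanent discontinuation only |

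Under SAP Panel 3, a date of permanent discontinuation exists only where a reason for it has been recorded. A subject whose IMP is merely suspended has no such date. No other rule in either document sets an assessment made under a prohibited treatment to non-response.

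**Step 2: reproduce the planning figures.** Protocol 14.1 plans on 19% responders for IGA 0/1 and 29% for EASI75. It gives standard errors of 3.44% and 3.98%, and half-widths of 6.74 and 7.80 points. Using SE = √(p(1−p)/n) and half-width = 1.96 × SE with n = 130:

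- IGA 0/1: √(0.19 × 0.81/130) = 3.44%; half-width 6.74 points.
- EASI75: √(0.29 × 0.71/130) = 3.98%; half-width 7.80 points.

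All four figures reproduce. The gap does not affect them.

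**Step 3: effect per subject.** Moving one responder to non-response lowers the rate by:

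- Overall: 1/130 = 0.77 points.
- Adults: 1/(130 − 30) = 1.0 point.
- Adolescents: about 1/30 = 3.3 points.

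**Step 4: illustration.** The number k of affected responders is an assumption; the documents give none. The starting counts are the planned rates rounded to whole subjects (25 and 38 of 130). The intervals are Wilson, as in SAP 5.1.

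| k | Shift (points) | IGA 0/1 | EASI75 |
|---|---|---|---|
| 0 | 0 | 19.2% (13.4 to 26.8) | 29.2% (22.1 to 37.6) |
| 1 | 0.77 | 18.5% (12.7 to 26.0) | 28.5% (21.4 to 36.7) |
| 3 | 2.31 | 16.9% (11.4 to 24.3) | 26.9% (20.0 to 35.1) |
| 6 | 4.62 | 14.6% (9.6 to 21.7) | 24.6% (18.0 to 32.7) |

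To shift the rate by a full planned half-width takes 9 responders for IGA 0/1 (6.74/0.769 = 8.8) and 11 for EASI75 (7.80/0.769 = 10.1). Among 30 adolescents, one responder moves IGA 0/1 from 6/30 = 20.0% (9.5 to 37.3) to 5/30 = 16.7% (7.3 to 33.6).

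**The case against.** The strongest reply is that both treatments are prohibited, so only protocol deviators are affected. Important deviations will be described in the CTR, and decisions on subject data will be documented in the analysis set definition document. There is no formal test and no success threshold. Two parts of this stand: the cases may be few, and they would not be invisible. It does not close the gap, because neither document contains a pre-specified response rule for these cases. Nor is the algorithm confined to permitted rescue: it lists dupilumab, although Protocol 9.5 disallows biological rescue throughout.

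The corticosteroid case is weaker than the phototherapy case:

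- Asthma appears as a medical-history item, but nothing shows how often a course of systemic corticosteroids would be needed. Exclusion 24 already removes unstable disorders that could influence the findings.
- The last dose is at Week 14, so a course started after it suspends nothing.
- A subject suspended at or before Week 14 who never resumes may be recorded as permanently discontinued, and is then already a non-responder.
- The treatment-failure half of the SAP's rationale does not fit a course given for another disease; only the attribution half does.

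A reader might also infer that the gap can only inflate the rates. That is so only when they are compared with a rule that counts these subjects as failures. Against response on tralokinumab alone the direction is not certain. Some of these subjects would have responded anyway, and a suspension of IMP could itself lower response.

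**Conclusion.** The gap is real and follows from the text of SAP 5.3 and Protocol 14.3.4. It is clearest for phototherapy given for AD: an AD treatment, prohibited on study and collected in the eCRF, that the rule cannot see. By the SAP's own attribution argument it belongs with rescue. For non-AD systemic corticosteroids the gap exists, but non-response in the primary analysis is a debatable estimand choice, and a sensitivity analysis is the proportionate answer.

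The size is 0.77 points per affected responder overall and about 3.3 points among adolescents, if enrolment is about 130 and 30. The total is unknown. It is small against the planned half-widths unless several responders are affected.

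Two further readings go beyond the documents. One is that the 4-week exclusions are there because of carry-over: Protocol 7.1 speaks only of wash-out, and the point does not need more. The other is that systemic immunosuppressants for any indication belong in the same rule: Protocol 9.7 prohibits them as systemic treatment for AD, so no parallel case is made for other indications.

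**What to change.** In SAP 5.3, logged in Panel 11:

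1. **Primary rule.** Treat phototherapy given for AD between first dose and the efficacy assessment as initiation of rescue treatment. Assessments after its start date count as non-response, and the same-day convention of Protocol 14.3.4 is kept. Identify it from both the concurrent-procedure and the concomitant-medication records, since Protocol 9.6 and 9.7 point to different forms. Apply the rule to all binary efficacy endpoints.
2. **Sensitivity analysis.** For the same endpoints, count as non-response any assessment made within 4 weeks after systemic corticosteroid use for any indication. The window is the protocol's own pre-baseline interval. Code H02 without the indication condition, checked against the recorded route of administration, would identify these courses.
3. **Listing.** List every subject reclassified under 1 or 2, with dates and indication.

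The cost is a few lines of SAP text and some programming on data already collected. The response rate may be slightly lower. In the sensitivity analysis, some genuine responders with a short non-AD course will count as failures, which is why it should not replace the primary analysis. Tanning for non-AD reasons may not be in the procedure record, so rule 1 does not claim to cover it. The change should be made before the adult interim lock; if made later, it should be labelled as such. It is an analysis rule only and leaves treatment and stopping rules as they are.
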